# 6.5. Assessment of Subject Compliance with Study Drug

Study staff will be present for and during all study drug administrations. Visual inspection by study staff of the complete infusion is expected and will be appropriately recorded in the eCRF. It is important to document that the entire 200 mL infusion is administered with each dose. All interruptions or premature terminations of infusion will be documented.

## 6.6. Concomitant Medications/Treatments

Medications to treat any AEs the subject experiences during the trial are permitted. All information on concomitant medications will be recorded on the subject's eCRF and will include the name of the procedure or drug and duration of the treatment (start/stop times), dosages, and route. The intermittent intake of acetaminophen (maximum 2 g/day) is permitted throughout the trial if approved by the Site PI. Subjects are required to refrain from the use of all prescription medications for at least 30 days before administration of the first dose of study drug on Day 1 until the last PK sample is taken. The consumption of beverages containing alcohol is prohibited for 48 hours before Baseline (Day -1 to Day 1) until completion of the Treatment Phase. The consumption of caffeine is prohibited for 7 days prior to Baseline (Day -1 to Day 1) and during the Treatment Phase. Herbal supplements and over-the-counter meds (except acetaminophen at doses  $\leq 2$  g/day) must be discontinued 7 days before the first dose of study drug until completion of the Treatment Phase. The use of illegal drugs is prohibited within the 6 months prior to Baseline (Day -1 to Day 1) and is not permitted while subjects are enrolled in this study. A urine drug screen will be performed at Screening. If a subject is unable to comply with the restrictions described above, the subject's continued participation in the trial will be re-evaluated by the investigator.

DMID/NIAID/NIH

CONFIDENTIAL

DMID eCTD Compliant Interventional Protocol Template and Instructions, Version 2.0, Dated August 10, 2017

# 7. STUDY SCHEDULE

## 7.1. Screening (Day -30 to Day -1)

Subjects will be screened within 30 days before Enrollment/Baseline (Day -1 to Day 1). A sufficient number of individuals will be screened to identify 40 subjects for enrollment that fulfill all entry criteria in order to obtain 30 evaluable subjects at the end of the trial. After the subject has signed the IRB-approved ICF, the following evaluations will be performed and/or recorded in the eCRF:

- Demographics (date of birth, gender, and race/ethnicity)
- Complete medical history and prior medication history to include all drugs taken (including nonprescription and herbal products) within 30 days before screening procedures
- Physical exam to include the following organs and organ systems: vital signs (temperature, blood pressure, respiratory rate, heart rate, peripheral oxygen saturation), skin, head and neck, lungs, heart, liver, spleen, extremities, lymph nodes, and nervous system.
- Record history of alcohol (within prior 6 months) and tobacco use (lifetime)
- Height and weight to determine BMI
- Standard 12-lead ECG
- Laboratory tests (urine and blood specimens) as outlined in Appendix A
- Urine drug screen, urine cotinine, and alcohol test (breathalyzer)
- Serum pregnancy test for females of childbearing potential
- Collect birth control method and counsel subjects on acceptable contraceptive measures
- Counsel participants to avoid consumption of non-prescription medications, vitamins, licorice (in large amounts), caffeine or dietary or herbal supplements in the 7 days prior to confinement and to avoid consumption of beverages and foods containing alcohol for 48 hours prior to confinement
- Confirm all inclusion and exclusion criteria are fulfilled
- SARS-CoV-2 (COVID-19) test will occur within 72 hours prior to admission at the Screening Visit (Day -30 to Day -1) if Screening Visit occurs between (Day -3 to Day -2)

# 7.2. Enrollment/Baseline (Day -1 to Day 1)

Subjects will be admitted to DEPRU on Day -1 or Day 1 before the first dose of study drug on Day 1. After admission to DEPRU, the following Enrollment/Baseline tests and evaluations will be performed.

DMID/NIAID/NIH

All Enrollment/Baseline tests and evaluations will be performed within 36 hours of randomization to a bronchoscopy time.

- Physical exam to include the following organs and organ systems: vital signs (temperature, blood pressure, respiratory rate, heart rate, peripheral oxygen saturation), skin, head and neck, lungs, heart, liver, spleen, extremities, lymph nodes, and nervous system
- Weight
- Review changes in the subject's medical history since screening
- Laboratory tests as outlined in Appendix A
- Urine pregnancy test for females of childbearing potential
- Counsel subjects on acceptable contraceptive measures
- Urine drug screen, urine cotinine, and alcohol breath test (breathalyzer)
- Review prior concomitant medication history since screening
- Record non-pharmacologic treatments/procedures within 72 hours before enrollment in the eCRF
- Confirm all inclusion and exclusion criteria are fulfilled
- Standard 12-lead ECG
- Randomize to a bronchoscopy time
- Place two peripheral IVs
- SARS-CoV-2 (COVID-19) test will occur within 72 hours prior to admission at the Baseline Visit (Day -1 to Day 1) if test was not administered during Screening Visit

## 7.3. Day 1 to Day 2

- Administer study drug to subjects every 8 hours for a total of 3 doses.
- Obtain vital signs, including heart rate, blood pressure, temperature, respiratory rate and peripheral oxygen saturation before each dose of study drug, and at approximately 0.5, 1, 2, and 5 hours after the start of each dose of study drug (T0 = time of each infusion start)
- Review and record any AEs and SAEs
- Review and record any concomitant medications, vitamins and herbal supplements
- Perform a standard 12-lead ECG within 2 hours after the third (last) dose of study drug

#### DMID/NIAID/NIH

#### CONFIDENTIAL

- Obtain PK blood samples at 15 timepoints: before (within 10 minutes) the first, second, and third doses of study drug, at 30 minutes (during infusion), 1 hour (within 5 minutes after the end of infusion), 1 hour 15 minutes, 2, and 5 hours from the start time of the first infusion of ZTI-01, and at 30 minutes (during infusion), 1 hour (within 5 minutes after the end of infusion), 1 hour 15 minutes, 2, 5, 8, and 12 hours from the start time of the third (last) infusion of ZTI-01
- Measurement of sodium, potassium, magnesium, calcium, and phosphorus approximately 2 hours prior to the assigned bronchoscopy timepoint
- A standardized bronchoscopy with BAL sampling will be performed at single timepoint based on each subject's schedule assignment at either 30 minutes, 1 hour 15 minutes, 2, 5, or 8 hours after the start time of the third (last) infusion of ZTI-01
- Collect a blood sample to measure serum urea concentration just before or during bronchoscopy

# 7.4. Day 2 (Day of Discharge from DEPRU)

- Laboratory tests and urinalysis as outlined in Appendix A
- Review and record any AEs and SAEs
- Review and record any concomitant medications, non-pharmacologic treatments or procedures
- Perform a physical exam to include the following organs and organ systems: vital signs (temperature, blood pressure, respiratory rate, heart rate, peripheral oxygen saturation), skin, head and neck, lungs, heart, liver, spleen, extremities, lymph nodes, and nervous system; measure weight before discharge

# 7.5. Day 3 (Telephone Follow-up Call)

A telephone call follow-up will be conducted the day following each subject's discharge from DEPRU to ask about subject's clinical status, concomitant medications, and AEs/SAEs. In the event of ongoing or new AEs/SAEs, subjects may be asked to return to DEPRU for evaluation at the investigator's discretion. Ongoing AEs/SAEs will be followed until resolved or stable/improving over two assessments and no further intervention is required.

# 7.6. Early Termination Visit

If the subject is prematurely discontinued from the trial, the same exit procedures as those performed on Day 1 or 2 will be performed before discharging the subject from DEPRU. If no clinical or laboratory abnormalities are observed, subjects are considered to have completed the protocol and will exit the trial. Additional follow-up visits will be scheduled if a subject has an ongoing clinically significant abnormality at this visit and/or the clinical laboratory evaluations reveal a clinically significant laboratory abnormality, as deemed appropriate by the investigator or designee. Clinically significant laboratory

DMID/NIAID/NIH

abnormalities will be monitored periodically until resolution or until they are considered irreversible, or until there is a satisfactory explanation for the changes observed.

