#### 5.3.2. Reasons for Withdrawal and Discontinuation of Study Product Administration

Subjects may voluntarily withdraw their consent for study participation at any time without penalty or loss of benefits to which they are otherwise entitled.

An investigator may also withdraw a subject from receiving the study drug for any reason. Follow-up safety evaluations will be conducted, if the subject agrees. If a subject withdraws or is withdrawn before completion of the study, the reason for this decision will be recorded in the eCRF. The reasons might include, but are not limited to the following:

- Subject no longer meets eligibility criteria
- Subject becomes noncompliant

- Subjects develops a medical disease or condition, or new clinical finding(s), for which continued participation, in the opinion of the investigator, might compromise the safety of the subject, interfere with the subject's successful completion of this study, or interfere with the evaluation of responses
- Subject is lost to follow-up
- Subject becomes pregnant

The investigator will be explicit regarding study follow-up (e.g., safety follow-up) that might be carried out despite the fact the subject will not receive further study drug. If the subject consents, every attempt will be made to follow all AEs through resolution. The procedures that collect safety data for the purposes of research will be included in the original ICF or the investigator may seek subsequent informed consent using an IRB/IEC-approved ICF with the revised procedures.

The investigator will inform the subject that data already collected will be retained and analyzed even if the subject withdraws from the trial.

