#### 5.3.3. Handling of Withdrawals and Discontinuation of Administration

Subjects who discontinue will be asked about the reason(s) for their discontinuation and about the presence of any AEs. If possible, they will be seen and assessed by an investigator(s). AEs will be followed to resolution and/or until deemed stabilized by the investigator. Subjects who discontinue may be subject to replacement as described in Section 5.3.4. If subjects are not evaluable and thus are replaced, their samples will be discarded. If the subject received any amount of study drug, they will be encouraged to follow up for safety.

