# 9.2. Methods and Timing for Assessing, Recording, and Analyzing Safety Parameters

#### 9.2.1. Adverse Events

ICH E6 defines an AE as any untoward medical occurrence in a patient or clinical investigation subject administered a pharmaceutical product, and that does not necessarily have a causal relationship with this treatment. An AE can therefore be any unfavorable and unintended sign (including a clinically significant laboratory abnormality), symptom, or disease temporally associated with use of the study drug, whether or not it is deemed related to the study drug. The occurrence of an AE may come to the attention of study personnel during study visits and interviews of a study subject presenting for medical care, or upon review by a study monitor. The period of observation for AE reporting will begin on Day 1 at the time of first dosing and continue through the final visit, a follow-up call on Day 3.

All AEs including local and systemic reactions not meeting the criteria for SAEs will be captured on the appropriate eCRF. Information to be collected includes event description, time of onset, clinician's assessment of severity, relationship to study drug (assessed only by those with the training and authority to make a diagnosis), outcome, action taken, and time of resolution/stabilization of the AE. All AEs occurring while on study will be documented appropriately regardless of relationship. All AEs will be followed until they adequately resolve or are determined by the PI to be medically stable (stable or improving over two assessments and no further intervention required). Any medical condition that is present at the time that the subject is screened will be considered as a baseline finding and not reported as an AE. However, if its Grade increases at any time during the trial such that it meets the AE definition specified above, it will be recorded as an AE.

All systemic and laboratory AEs will be graded using the Adverse Event Toxicity Grading Scale (Appendix B). Laboratory toxicity grading will be determined by using these tables as modified for the study to accommodate the reference range of the Central Laboratory and the acceptable ranges used in

DMID/NIAID/NIH

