## 9.3. **Reporting Procedures**

AEs will be reported from the time of dosing on Day 1 through the Telephone Follow-up Interview on Day 3.

All AEs will be followed until resolution. Resolution of an AE is defined as the return to pretreatment status or stabilization of the condition with the expectation that it will remain chronic.

All AEs and SAEs will be reported, whether or not that are deemed causally related to the study drug. All AEs and SAEs will be recorded in the eCRF.

SAEs will be followed until resolution even if this extends beyond the study-reporting period.

CONFIDENTIAL

DMID/NIAID/NIH

The Site PI is responsible for informing the IRB of the SAE as per local requirements. DMID will be responsible of informing the US Regulatory Authority of the SAE as per federal requirements.

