# 14.6. Study Discontinuation

If the trial is discontinued, subjects who have signed the ICF and are administered study drug, will continue to be followed for safety for the duration of the scheduled follow-up period. No further study drug will be administered.

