9.3. Adverse Events

TEAEs will be collected from the start of the first infusion on Day 1 through the Telephone Follow-Up Interview on Day 3. When calculating the incidence of AEs (i.e., on a per subject basis), each subject will only be counted once at the highest severity recorded and any repetitions of AEs within a subject will be ignored. Denominators for percentages are the number of subjects in the Safety Population.

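### Protocol 7.6 labels a clean early exit as protocol completion, which conflicts with AE collection through the Day 3 call, and the SAP's any-time AE percentage cannot show the gap

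*Protocol*

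**What the plan says.** Protocol 7.6 requires exit procedures before a prematurely discontinued subject leaves the unit, and then says: "If no clinical or laboratory abnormalities are observed, subjects are considered to have completed the protocol and will exit the trial". Further visits are scheduled only for ongoing clinically significant findings. The section does not mention the Day 3 call.

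Other sections describe a longer observation period:

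- Protocol 7.5: "A telephone call follow-up will be conducted the day following each subject's discharge from DEPRU". It makes no exception for early exits.
- Protocol 9.2.1: "The period of observation for AE reporting will begin on Day 1 at the time of first dosing and continue through the final visit", which it identifies as the Day 3 follow-up call. Section 9.3 agrees ("AEs will be reported from the time of dosing on Day 1 through the Telephone Follow-up Interview on" Day 3), as do 3.2 and Appendix A footnote b.
- Protocol 5.3.2, on subjects withdrawn from study drug: "Follow-up safety evaluations will be conducted, if the subject agrees".
- Protocol 5.3.3: "If the subject received any amount of study drug, they will be encouraged to follow up for safety".

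In the SAP, anyone who starts the first infusion is in the Safety Population (6.3.1). Section 9.3 sets the AE denominator: "Denominators for percentages are the number of subjects in the Safety Population". No missing safety value is imputed, although the amount of missing data and the reasons are to be summarized (6.5). Table 5 has its own row for Day 3 follow-up, and Listing 1 shows early terminations and treatment discontinuations.

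**The concern.** The main safety outcome is the occurrence of AEs over a fixed window, from first dosing to the Day 3 call. Section 7.6 is the only section written for the early-termination visit, and for a clean exit it gives an endpoint earlier than that window. A site following it literally could stop collecting AEs at discharge.

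Two things are at stake. The first is observation. A normal check at exit does not show that nothing happens afterwards; section 2.3.1, for example, asks for colitis to be considered when diarrhea occurs during or after therapy. The second is classification. A subject who stopped early could be entered as a completer, although Table 5 and Listing 1 are meant to separate the two.

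Early exits are foreseeable. Section 9.5 stops dosing and procedures for an individual with a Grade 2 or higher electrolyte value before bronchoscopy. If the values are normal again at the exit check, the literal wording of 7.6 could apply to that subject.

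**Working it through.** **Step 1: follow one subject through the text.** Take a dosed subject who is discontinued on Day 1, is discharged that day with normal exit checks, and agrees to follow-up.

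- Under 7.6, the subject has completed and has left the trial at discharge.
- Under 7.5, the subject is called the day after discharge, which here is Day 2.
- Under 9.2.1 and 9.3, AEs are collected through the Day 3 call.
- Under 5.3.2, safety evaluations continue because the subject agrees.
- Under SAP 6.3.1 and 9.3, the subject counts as one full unit in the any-time AE denominator.
- Under SAP Table 5 and Listing 1, the subject is an early termination without Day 3 follow-up, unless the 7.6 label is carried into the data.

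These cannot all hold. Section 7.5 does not fully repair 7.6 either, because for a Day 1 discharge its call falls before the AE window closes.

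**Step 2: reproduce the plan's own safety figure.** Protocol Table 8 gives the probability of at least one event in n = 30, which is 1 − (1 − p)^30.

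| True rate p | Table 8 | Recomputed |
|---|---|---|
| 0.1% | 3% | 2.96% |
| 0.5% | 14% | 13.96% |
| 1% | 26% | 26.03% |
| 2% | 45% | 45.45% |
| 5% | 79% | 78.54% |
| 7% | 89% | 88.66% |
| 10% | 96% | 95.76% |
| 15% | 99% | 99.24% |

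All eight entries match. The formula treats every subject as observed for the whole window.

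**Step 3: size the effect of missing contact.** Suppose m of n dosed subjects exit early with no later contact, and a share f of their event risk falls after exit. Assume they carry the same full-window risk p as everyone else.

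- Expected observed incidence ÷ true incidence = [(n − m)p + m·p(1 − f)] ÷ (n·p) = 1 − m·f/n
- P(at least one event observed) = 1 − (1 − p)^(n − m) × (1 − p(1 − f))^m

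The documents give neither m nor f, so both are assumed. With n = 30, as in Table 8:

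| m | f | 1 − m·f/n | Relative fall | P(at least one), p = 5% |
|---|---|---|---|---|
| 0 | – | 1.000 | 0% | 78.5% |
| 1 | 0.25 | 1 − 0.25/30 = 0.992 | 0.8% | 78.3% |
| 2 | 0.50 | 1 − 1/30 = 0.967 | 3.3% | 77.4% |
| 4 | 0.50 | 1 − 2/30 = 0.933 | 6.7% | 76.2% |
| 4 | 0.75 | 1 − 3/30 = 0.900 | 10.0% | 74.9% |

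Detection probability at a true 5% rate falls by 0.3 to 3.6 percentage points. If all 40 enrolled subjects were dosed, the same extremes give 1 − 0.25/40 = 0.994 and 1 − 3/40 = 0.925, a relative fall of 0.6% to 7.5%.

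**The case against.** The strongest reply is that 7.6 never says the call is dropped. Section 7.5 ties the call to discharge, and 7.6 describes what happens before discharge, so the trigger still occurs. Sections 5.3.2 and 5.3.3 also provide for safety follow-up. This stands: a reader might infer that the protocol exempts these subjects from the Day 3 call, but the documents support only a conflict.

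Other stronger readings also fail:

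- **That subjects with tolerability problems get the least observation.** The sentence covers only exits with no abnormality. Ongoing clinically significant findings lead to further visits.
- **That 7.6 creates the denominator problem.** The denominator rule is the SAP's and applies to anyone who misses the call. What 7.6 can add is unobserved time.
- **That the gap would be invisible.** Table 5, Listing 1 and the missing-data summary in SAP 6.5 would partly show it, and Table 12 limits its interval denominators to subjects who started that infusion. These displays depend on correct classification, which the 7.6 label undermines, and the any-time column has no such limit.
- **That 14.6 contradicts 7.6.** That section concerns stopping the whole trial, when dosed subjects "will continue to be followed for safety for the duration of the scheduled follow-up period". It is a contrast: a single early stop could receive less follow-up than a trial-wide one.
- **That post-bronchoscopy cough or fever would be missed in a subject stopped before Dose 2.** Bronchoscopy takes place only after Dose 3 starts, so such a subject never has one.

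**Conclusion.** The point holds as an internal conflict that should be corrected. As written, 7.6 labels a discontinued subject as a completer and can be followed in a way that ends AE observation before the stated window closes. The any-time AE percentage then cannot separate subjects without events from subjects not observed.

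The likely numerical effect is modest: a relative fall of 0.8% to 10% in expected AE incidence. That range assumes 1 to 4 early exits among 30, 25-75% of their risk after exit, equal underlying risk, and no later contact at all. If the call is made and covers the rest of the window, the effect is zero and Table 8 stands. A reader might infer that the reported AE rates will be biased low by a known amount. The documents do not support this, because they give neither the number nor the timing of early exits. The study is also descriptive, with no formal hypothesis.

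**What to change.** 1. **Protocol 7.6:** remove the statement that a subject with clean exit checks has completed the protocol and leaves the trial. Reconcile the section with 7.5, 9.2.1, 9.3, 5.3.2 and 5.3.3, so that AE and SAE collection for dosed subjects who agree runs to the end of the stated AE window. Keep the condition of agreement, since consent may be withdrawn. The reconciliation should also settle when the call is made after a Day 1 discharge.
2. **Disposition:** record these subjects as early terminations in SAP Listing 1, and count them in Table 5's Day 3 row only if the contact took place.
3. **SAP 9.3 and the any-time column of Table 12:** report beside the AE percentages the number of dosed subjects without a Day 3 contact.

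The cost is one sentence in the protocol, one footnote in the SAP and at most a few telephone calls. Dosing and the sample size are unaffected.

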## 7.7. Unscheduled Visit (if needed)

- Review and record any AEs and/or SAEs
- Review and record any concomitant medications, non-pharmacologic treatments or procedures
- Perform a physical exam to include the following organs and organ systems: vital signs (temperature, blood pressure, respiratory rate, heart rate, peripheral oxygen saturation), skin, head and neck, lungs, heart, liver, spleen, extremities, lymph nodes, and nervous system
- Obtain a standard 12-lead ECG at the investigator's discretion
- Other studies as clinically indicated at the investigator's discretion

DMID/NIAID/NIH

CONFIDENTIAL

